Skewed numerical will be presented presented as median (interquartile range) and inter-group differences were compared non-parametrically using the Kruskal-Wallis test.

Categorical variables were presented as number (%) and differences will be compared using Fisher's exact test.

Correlations among numerical variables will be tested non-parametrically using the Spearman rank correlation.

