Figure (6): Box plot showing the immature platelet count (IPC) in patients with SPE/HELLP or TTP/HUS and normal controls. Box represents the range from the first to third quartile (interquartile range). Line inside the box represents the median (second quartile). Whiskers represent the range between the minimum and maximum values excluding outliers (rounded markers).

Assessment of Immature Platelet Fraction in Pregnancy-Associated Thrombotic Microangiopathy: (Results)

[figure not shown]

Figure (7): Box plot showing the immature platelet fraction (IPF) in patients with SPE/HELLP or TTP/HUS and normal controls. Box represents the range from the first to third quartile (interquartile range). Line inside the box represents the median (second quartile). Whiskers represent the range between the minimum and maximum values.

Assessment of Immature Platelet Fraction in Pregnancy-Associated Thrombotic Microangiopathy: (Results)

Table (6): Prevalence of a low platelet count, high IPF, or high schistocyte count among patients with SPE/HELLP or TTP/HUS and normal controls

Variable	SPE/HELLP (n=24)	TTP/HUS (n=13)	Control (n=20)	P-value¶
Low total platelet count (<100,000/mm ³)	9 (37.5%)	11 (84.6%)	0 (0.0%)	<0.001
High IPF (>11.2%) (Machin, 2010)	14 (58.3%)	10 (76.9%)	5 (25.0%)	0.008
High schistocyte count (>0%) (Gina et al.,2011)	14 (58.3%)	11 (84.6%)	0 (0.0%)	<0.001

Data are number (%).

¶Fisher's exact test.

[figure not shown]

Figure (8): Prevalence of a low platelet count, high IPF, or high schistocyte count among patients with SPE/HELLP or TTP/HUS and normal controls.

Table (7): Receiver-operating characteristic (ROC) curve analysis for discrimination between patients with TTP/HUS or SPE/HELLP using the IPF or schistocyte count

Marker

Assessment of Immature Platelet Fraction in Pregnancy-Associated Thrombotic Microangiopathy: (Results)

Index	IPF	Schistocyte count
Sample size	37	37
Positive group (TTP/HUS)	13 (35.1%)	13 (35.1%)
Negative group (SPE/HELLP)	24 (64.9%)	24 (64.9%)
Area under the ROC curve (AUC)	0.692 (0.519 to 0.833)	0.771 (0.603 to 0.893)
z statistic	2.028	3.022
P-value	0.043¶	0.003¶
Associated cut-off criterion	>15.9 %	>4.6 %
Sensitivity (%)	76.92 (46.2 - 95.0)	61.54 (31.6 - 86.1)
Specificity (%)	66.67 (44.7 – 84.4)	91.67 (73.0 – 99.0)
Positive predictive value (PPV, %)	55.6 (30.8 - 78.5)	80.0 (44.4 - 97.5)
Negative predictive value NPV, %)	84.2 (60.4 - 96.6)	81.5 (61.9 - 93.7)

Diagnostic indices are presented as value (95% CI).

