Assessment of Immature Platelet Fraction in Pregnancy-Associated Thrombotic Microangiopathy: (Results)

All study population	57	0.466	0.0003
TMA	37	0.231	0.169
SPE/HELLP	24	0.190	0.375
TTP/HUS	13	-0.058	0.851
Control	20	0.000	-

[figure not shown]

Figure (15): Scatter plot showing the correlation between the IPF and schistocyte count in the whole study population. Fitted lines represent local regression smoothing (LOESS) trend lines.

Assessment of Immature Platelet Fraction in Pregnancy-Associated Thrombotic Microangiopathy: (Results)

[figure not shown]

Figure (16): Scatter plot showing the correlation between the IPF and schistocyte count in patients with TMA or normal controls. Fitted lines represent local regression smoothing (LOESS) trend lines.

[figure not shown]

Figure (17): Scatter plot showing the correlation between the IPF and schistocyte count in patients with SPE/HELLP or TTP/HUS and normal controls. Fitted lines represent local regression smoothing (LOESS) trend lines.

The results of the present study are shown in tables (14 -22) and figures (18-29).

✚ Comparison between patients with SPE/HELLP or TTP/HUS and normal controls regarding demographic features:

Assessment of Immature Platelet Fraction in Pregnancy-Associated Thrombotic Microangiopathy: (Results)

There was significant difference between the three studied groups regarding maternal age ($P < 0.05$) and high significant difference between the three groups regarding gestational age ($P < 0.001$). However, there was no significant difference between parity and previous abortions ($P > 0.05$). On applying Schéffé post-hoc test revealed no statistically significant difference among the three groups regarding maternal age ($P > 0.05$). However, regarding gestational age, the Schéffé test has revealed a significant difference between either patient group (SPE/HELLP or TTP/HUS) versus control group ($P < 0.05$ for each) (**Table 14**).

Assessment of Immature Platelet Fraction in Pregnancy-Associated Thrombotic Microangiopathy: (Results)

Table (14): Characteristics of patients with SPE/HELLP or TTP/HUS and normal controls

Variable	SPE/HELLP (n=24)	TTP/HUS (n=13)	Control (n=20)	F/ χ^2	DF	p-value
Age (years)	29.5 ± 5.6	25.3 ± 4.5	26.0 ± 4.6	4.086	2, 54	0.022¶†
Parity						
P0	6 (25.0%)	2 (15.4%)	5 (25.0%)	0.213	1	0.645§
P1	5 (20.8%)	7 (53.8%)	5 (25.0%)			
P2	8 (33.3%)	2 (15.4%)	6 (30.0%)			
P3	2 (8.3%)	1 (7.7%)	3 (15.0%)			

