Comparison of the receiver-operating characteristic (ROC) curves between IPF-% or schistocyte count for discrimination between patients with TMA and normal controls revealed no significant difference between IPF and schistocyte count regarding discrimination between patients with TMA and controls ($P > 0.05$) (Table 21), (Figure 28).

Table (21): ROC curves for discrimination between patients with TMA and normal controls using the IPF or schistocyte count

Index	IPF-%	Schistocyte count	Difference	z	P-value¶
Area under ROC (AUC)	0.820 (0.695 to 0.909)	0.838 (0.716 to 0.922)	0.018 (-0.105 to 0.142)	0.290	0.7722

Diagnostic indices are presented as value (95% CI).

¶DeLong method

Assessment of Immature Platelet Fraction in Pregnancy-Associated Thrombotic Microangiopathy: (Results)

[figure not shown]

Figure (28): ROC curves for discrimination between patients with TMA and normal controls using the IPF or schistocyte count.

✚ Correlation between IPF and schistocytes count with different parameters

no significant correlation was found between the IPF-% and schistocytes count in patients with SPE/HELLP, or TTP/HUS, as well as the whole TMA study group (**Figure 29**), (**Table 22**).

Table (22): Correlation between the IPF-% and schistocytes count in whole study population, patients with TMA, SPE/HELLP, or TTP/HUS, and normal controls

	Correlation between IPF % and schistocyte count		
Group	Number	Spearman rho (ρ)	P-value
TMA	37	0.231	0.169

Assessment of Immature Platelet Fraction in Pregnancy-Associated Thrombotic Microangiopathy: (Results)

SPE/HELLP	24	0.190	0.375
TTP/HUS	13	-0.058	0.851

[figure not shown]

Figure (29): Scatter plot showing the correlation between the IPF and schistocyte count in patients with SPE/HELLP or TTP/HUS.

IPF-% and schistocytes counts in TTP/HUS and SPE/HELLP using multivariate analysis

Assessment of Immature Platelet Fraction in Pregnancy-Associated Thrombotic Microangiopathy: (Results)

Multivariable binary logistic regression analysis was used for discrimination between patients with TTP/HUS or SPE/HELLP using the IPF-% and schistocyte count combined. Both IPF-% (odds ratio, 1.11; 95% CI, 1.010 to 1.220; $p=0.031$) and schistocyte count (odds ratio, 1.113; 95% CI, 1.016 to 1.219; $p=0.022$) were independent predictors for TTP/HUS.

Table (23): Multivariable binary logistic regression analysis for discrimination between patients with TTP/HUS or SPE/HELLP using the IPF and schistocyte count combined

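### Table 13's whole-population IPF-schistocyte correlation (0.466, P=0.0003) mostly reflects differences between the diagnostic groups; adjusted for group, the rank correlation is about 0.1

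*SAP*

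**What the plan says.** The Protocol's statistical methods section plans one method: "Correlations among numerical variables will be tested non-parametrically using the Spearman rank correlation". It does not say whether the groups are to be pooled, separated or adjusted for.

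SAP Table (13) gives five rows. The pooled rows are "All study population 57 0.466 0.0003" and "TMA 37 0.231 0.169". The single-group rows are "SPE/HELLP 24 0.190 0.375", "TTP/HUS 13 -0.058 0.851" and "Control 20 0.000", the last with a dash for P.

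Table (22) repeats only the TMA, SPE/HELLP and TTP/HUS rows, although its title still names the whole population and the controls. The sentence before it reports no significant correlation in either patient group, "as well as the whole TMA study group". No confidence interval is given for any rho, and no group-adjusted correlation is reported.

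Tables (4), (5), (15) and (16) report that all three pairs of groups differ significantly on both schistocyte count and IPF-%.

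**The concern.** When groups differ in the same direction on two variables, pooling them creates a correlation between the variables whether or not they move together inside any group. Here controls are lowest and TTP/HUS women highest on both markers. No single group shows a rho near 0.466.

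The only significant correlation printed may thus largely restate that the groups differ, which Tables (4) and (5) already show. A reader of Table (13) could take P=0.0003 as evidence that IPF-% tracks schistocyte count. The quantity that would show this, the association given diagnosis, is missing. The within-group values lack intervals, so the reader cannot see how little they rule out.

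**Working it through.** **Inputs.** Rho and n from Table (13). AUCs for TTP/HUS versus SPE/HELLP from Table (7): "Area under the ROC curve (AUC) 0.692 (0.519 to 0.833) 0.771 (0.603 to 0.893"), IPF first. AUCs for TMA versus control from Table (9): 0.820 and 0.838. Kruskal-Wallis H: 18.897 for IPF-% (Table 5) and 27.186 for schistocytes (Table 4). Women with a count above zero: 14/24, 11/13 and 0/20 (Table 6), so 32 of 57, and 12 of 37, are tied at zero. Ties other than at zero are assumed absent.

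**1. Printed P values.** With t = rho × √((n−2)/(1−rho²)):
- n=57: t = 3.906, P = 0.00026 (printed 0.0003)
- n=37: P = 0.169 (printed 0.169)
- n=24: P = 0.374 (printed 0.375)
- n=13: P = 0.851 (printed 0.851)

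The printed figures reproduce; the small gap at n=24 is rounding of rho.

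**2. Group mean ranks among 57.** The mean-rank difference between two groups is (AUC − 0.5) × N.
- *IPF-%.* TMA minus control = 0.320 × 57 = 18.24. Control mean rank = 29 − (37/57) × 18.24 = 17.16; TMA = 29 + (20/57) × 18.24 = 35.40. H gives a between-group sum of squares of 18.897 × 57 × 58/12 = 5206.1. The TMA-control split uses 4319.2, leaving 886.9 = (24 × 13/37) × d², so d = 10.26. Mean ranks: SPE/HELLP 31.80, TTP/HUS 42.05.
- *Schistocytes.* Among the 37, mean ranks are 19 − (13/37) × 0.271 × 37 = 15.48 and 19 + (24/37) × 0.271 × 37 = 25.50. Adding 20 controls at zero raises each non-zero rank by 20 and each tied-zero rank by 10 (6.5 to 16.5). Mean ranks: SPE/HELLP 31.31, TTP/HUS 43.97, control 16.50.

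**3. Check of the reconstruction.** The schistocyte mean ranks give H = 22.376/0.8232 = 27.18 (printed 27.186). The TMA-control AUC is 0.5 + (25/37)/2 = 0.838 (printed 0.838). Both fit all 20 controls at zero.

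**4. Whole population.** Total rank sums of squares are 15428 (IPF-%) and 12700 (schistocytes, after the tie deduction of 2728); the root of their product is 13997.7.
- Between-group cross-product: 155.1 + 2539.3 + 2960.0 = 5654.4
- Group separation alone: 5654.4/13997.7 = **0.404**, which is 87% of 0.466
- Adjusted rho: (0.466 × 13997.7 − 5654.4)/√((15428 − 5206.1) × (12700 − 6164.7)) = 868.5/8173.3 = **0.106**

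**5. The 37 TMA women.** Sums of squares are 4218 and 4075; the root of their product is 4145.9.
- Between-group cross-product: (13 × 24/37) × 7.104 × 10.027 = 600.7, giving 600.7/4145.9 = **0.145**, which is 63% of 0.231
- Adjusted rho: (957.7 − 600.7)/√(3792.4 × 3227.2) = 357.0/3498.4 = **0.102**
- 95% CI by Fisher z with standard error 1/√33: **−0.23 to 0.42**; P = 0.55

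**6. Second route.** The Fisher-z average of the two patient-group values, with weights n−3, is (21 × 0.1923 + 10 × (−0.0581))/31 = 0.1116, so rho = 0.111 (−0.24 to 0.43, P = 0.53). Counting the control value as a real zero gives 0.072.

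**7. Within-group 95% CIs.** SPE/HELLP −0.23 to 0.55; TTP/HUS −0.59 to 0.51.

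**The case against.** The strongest reply is that nothing said in the SAP depends on 0.466. The text never cites it, Table (13) prints the within-group values below it, and Table (22), the one with a narrative, leaves the row out. That stands. A reader might infer that the SAP claims the markers are correlated; its text says the opposite for every group it discusses.

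The TMA row also changes little. Adjustment moves it from 0.231 (P=0.169) to about 0.10 (P about 0.55), and the sentence on non-significance survives. A reader might infer that 0.231 is simply invalid. It is not: it describes how the two predictors correlate across the 37 women modelled in Table (23). It only needs its label.

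Nor do the documents offer the correlation as grounds for combining the markers. Tables (23) and (25) examine the combination directly, so the point does not undermine them.

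The plain Spearman plan was followed, and deleting a computed result can be less open than footnoting it. That too is fair, and a footnote suffices.

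What the reply does not answer is that a P value of 0.0003 stands in a results table for a quantity that is about 87% group separation, with no adjusted estimate beside it.

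**Conclusion.** The point holds as one of reporting. Group separation alone gives about 0.40 of the 0.466, and about 0.145 of the 0.231 in TMA; for the latter, calling it mostly between-group is a moderate statement at 63%. The group-adjusted rank correlation is about 0.1 (0.07 to 0.11 across methods).

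The interval to use is the patients-only one, about −0.23 to 0.42. A calculation on 57 women gives about −0.16 to 0.36, but that counts 20 controls who carry no information if all their counts are zero. It would be tempting to conclude that the markers are unrelated within groups. The interval does not support that: no association has been demonstrated, and a moderate one is not excluded.

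The result rests on rounded summary statistics, on no ties other than at zero, and on all controls being zero. Table (15) prints control schistocytes as 0.01 (0.0 to 0.03) where Table (4) prints 0.0 (0.0 to 0.0); H and the AUC fit all zeros. If that is so, the control rho is undefined, and 0.000 is not an estimate.

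**What to change.** - In Tables (13) and (22), report a Spearman correlation adjusted for diagnostic group in the 37 TMA women, with 95% CI, as the estimate of association.
- Keep 0.231 only as a labelled unadjusted value.
- Drop the 57-woman row and its P value, or footnote it as reflecting differences between groups.
- Give 95% CIs for the SPE/HELLP and TTP/HUS values.
- Reword the sentence before Table (22) to state the adjusted estimate and interval, as no demonstrated association rather than none.
- Reconcile the control schistocyte values in Tables (4) and (15). If all are zero, print the control rho as not estimable.
- Align Table (22)'s title with its rows.

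The cost is one re-analysis of data already held, plus edits to two tables and one sentence, and the reconciliation of the control values. If the 57-woman row is dropped, a printed P=0.0003 disappears; no stated conclusion changes.

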- Placental abnormalities like velamentous insertion.
- Multiple pregnancies.
- Known kidney disease.
- History of auto immune disease.

Ethical Considerations

An informed consent will be taken from each patient. The aim of the research was explained to patients. No harm was caused to patients as blood samples were routinely collected from patients.

Consent form:

Patient name:

Hospital number:

Information to the participant:

The procedure

- The results of your blood results and hospital data will be used in this clinical trial.
- An extra blood sample will be withdrawn at the time of diagnosis which is a simple procedure with no known complications.
- All your data and blood results, will saved confidentially and it will appear as a number in the results.
- The results of these investigation will not affect your management plan.

Methodology

An informed consent will be taken from each participant.

For all patients included in the study the following were done

1- Thorough history taking with special emphasis on:

- The gestational age will be estimated according to the last menstrual period and confirmed by a first trimesteric ultrasound.
- Past history to ensure the absence of any medical disorder included in exclusion criteria.

2- General, abdominal and local examination with particular emphasis on vital sign monitoring records.

Laboratory Investigations:

▪ **Haematological tests**

○ *Sampling:*

Five (5.0) ml of venous blood will be collected from each patient, it will be divided as follows:

- **Two (2.0) ml** added to an EDTA containing sterile tube for assessment of:
 - a) *Complete blood count (CBC)*, for estimation of hemoglobin concentration and platelet count using XE-2100® (Sysmex Corporation, Kobe, Japan) automated hematology system.
 - b) *Morphological assessment of different blood cells* with special emphasis on estimation of schistocyte counts (if present), achieved by microscopic examination of Romanowsky-stained PB smears prepared from an EDTA-anticoagulated PB sample. Schistocytes counting will be performed in at least 1000 RBCs in optimal areas of the film, with interpretation of results following the ICSH recommendations for identification, diagnostic value, and quantitation of schistocytes (**Zini et al., 2011**).
 - c) *Reticulocyte count*: by microscopic examination of supravitaly stained PB smear.

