¶DeLong method.

Assessment of Immature Platelet Fraction in Pregnancy-Associated Thrombotic Microangiopathy: (Results)

[figure not shown]

Figure (9): Receiver-operating characteristic (ROC) curve analysis for discrimination between patients with TTP/HUS or SPE/HELLP using the IPF.

Assessment of Immature Platelet Fraction in Pregnancy-Associated Thrombotic Microangiopathy: (Results)

[figure not shown]

Figure (10): Receiver-operating characteristic (ROC) curve analysis for discrimination between patients with TTP/HUS or SPE/HELLP using the schistocyte count.

Assessment of Immature Platelet Fraction in Pregnancy-Associated Thrombotic Microangiopathy: (Results)

Table (8): Comparison of the receiver-operating characteristic (ROC) curves for discrimination between patients with TTP/HUS or SPE/HELLP using the IPF-% or schistocyte count

Marker					
Index	IPF-%	Schistocyte count	Difference	z	P-value¶
Area under ROC (AUC)	0.692 (0.519 to 0.833)	0.771 (0.603 to 0.893)	0.079 (-0.171 to 0.328)	0.617	0.537

Diagnostic indices are presented as value (95% CI).

¶DeLong method.

[figure not shown]

Figure (11): Comparison of the receiver-operating characteristic (ROC) curves for discrimination between patients with TTP/HUS or SPE/HELLP using the IPF or schistocyte count.

Table (9): Receiver-operating characteristic (ROC) curve analysis for discrimination between patients with TMA and normal controls using the IPF-% or schistocyte count

Marker					
--------	--	--	--	--	--

Assessment of Immature Platelet Fraction in Pregnancy-Associated Thrombotic Microangiopathy: (Results)

Index	IPF	Schistocyte count
Sample size	57	57
Positive group (TMA)	37 (64.9%)	37 (64.9%)
Negative group (normal controls)	20 (35.1%)	20 (35.1%)
Area under the ROC curve (AUC)	0.820 (0.695 to 0.909)	0.838 (0.716 to 0.922)
z statistic	5.678	8.660
P-value	<0.0001¶	<0.0001¶
Associated cut-off criterion	>8.1 %	>0 %
Sensitivity (%)	86.49 (71.2 - 95.5)	67.57 (50.2 - 82.0)
Specificity (%)	65.00 (40.8 - 84.6)	100.00 (83.2 - 100.0)
Positive predictive value (PPV, %)	82.1 (66.5 - 92.5)	100.0 (86.3 - 100.0)
Negative predictive value (NPV, %)	72.2 (46.5 - 90.3)	62.5 (43.7 - 78.9)

Diagnostic indices are presented as value (95% CI).

¶DeLong method.

Assessment of Immature Platelet Fraction in Pregnancy-Associated Thrombotic Microangiopathy: (Results)

[figure not shown]

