Figure (12): Receiver-operating characteristic (ROC) curve for discrimination between patients with TMA and normal controls using the IPF.

Assessment of Immature Platelet Fraction in Pregnancy-Associated Thrombotic Microangiopathy: (Results)

[figure not shown]

Figure (13): Receiver-operating characteristic (ROC) curve for discrimination between patients with TMA and normal controls using the schistocyte count.

Assessment of Immature Platelet Fraction in Pregnancy-Associated Thrombotic Microangiopathy: (Results)

Table (10): Comparison of the receiver-operating characteristic (ROC) curves for discrimination between patients with TMA and normal controls using the IPF or schistocyte count

Index	Marker		Difference	z	P-value¶
	IPF	Schistocyte count			
Area under ROC (AUC)	0.820 (0.695 to 0.909)	0.838 (0.716 to 0.922)	0.018 (-0.105 to 0.142)	0.290	0.7722

Diagnostic indices are presented as value (95% CI).

¶DeLong method.

Assessment of Immature Platelet Fraction in Pregnancy-Associated Thrombotic Microangiopathy: (Results)

[figure not shown]

Figure (14): Comparison of the receiver-operating characteristic (ROC) curves for discrimination between patients with TMA and normal controls using the IPF or schistocyte count.

Assessment of Immature Platelet Fraction in Pregnancy-Associated Thrombotic Microangiopathy: (Results)

Table (11): Multivariable binary logistic regression analysis for the relation between the IPF-% and TTP/HUS with adjustment for the confounding effect of the gestational age

Variable	Regression coefficient (B)	SE for B	Wald	P-value	Odds ratio (OR)	95% CI for OR
IPF -%	0.084	0.041	4.105	0.043	1.088	1.003 to 1.179
Gestational age (weeks)	-0.064	0.087	0.539	0.463	0.939	0.792 to 1.112
Constant	-0.271					

Table (12): Multivariable binary logistic regression analysis for the relation between the schistocyte count and TTP/HUS with adjustment for the confounding effect of the gestational age

Variable	Regression coefficient (B)	SE for B	Wald	P-value	Odds ratio (OR)	95% CI for OR
Scistocyte count (%)	0.101	0.052	3.781	0.052	1.107	0.999 to 1.226
Gestational age (weeks)	-0.052	0.088	0.355	0.551	0.949	0.799 to 1.127
Constant	0.420					

Table (13): Correlation between the IPF and schistocytes count in whole study population, patients with TMA, SPE/HELLP, or TTP/HUS, and normal controls

Correlation between IPF-% and schistocyte count			
Group	Number	Spearman rho (ρ)	P-value

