- **Prevalence of a low platelet count (A-IPC):** There was high significant difference between the three groups regarding prevalence of a low platelet count ($P < 0.001$) (Table 17), (Figure 22).
- **Prevalence of high IPF-%:** There was significant difference between the three groups regarding prevalence of high IPF ($P < 0.05$) (Table 17), (Figure 22).
- **Prevalence of high schistocyte count:** There was high significant difference between the three groups regarding prevalence of high schistocyte count ($P < 0.001$) (Table 17), (Figure 22).

Table (17): Prevalence of a low platelet count, high IPF, or high schistocyte count among patients with SPE/HELLP or TTP/HUS and normal controls

Variable	SPE/HELLP (n=24)	TTP/HUS (n=13)	Control (n=20)	P-value¶
Low total platelet count ($< 100,000/\text{mm}^3$)	9 (37.5%)	11 (84.6%)	0 (0.0%)	< 0.001
High IPF-% ($> 11.2\%$) (Machin, 2010)	14 (58.3%)	10 (76.9%)	5 (25.0%)	0.008
High schistocyte count ($> 1\%$) (Gina et al., 2011)	14 (58.3%)	11 (84.6%)	0.01 (0.0%)	< 0.001

Data are number (%).

¶Fisher's exact test.

Assessment of Immature Platelet Fraction in Pregnancy-Associated Thrombotic Microangiopathy: (Results)

[figure not shown]

Figure (22): Prevalence of a low platelet count, high IPF, or high schistocyte count among the studied groups.

✚ Receiver-operating characteristic (ROC) curve analysis

Table (18): Receiver-operating characteristic (ROC) curve analysis for discrimination between patients with TTP/HUS or SPE/HELLP using the IPF or schistocytes count

Index	Marker
-------	--------

Assessment of Immature Platelet Fraction in Pregnancy-Associated Thrombotic Microangiopathy: (Results)

	IPF	Schistocyte count
Positive group (TTP/HUS)	13 (35.1%)	13 (35.1%)
Negative group (SPE/HELLP)	24 (64.9%)	24 (64.9%)
Area under the ROC curve (AUC)	0.692 (0.519 to 0.833)	0.771 (0.603 to 0.893)
z statistic	2.028	3.022
P-value	0.043¶	0.003¶
Associated cut-off criterion	>15.9 %	>4.6 %
Sensitivity (%)	76.92 (46.2 - 95.0)	61.54 (31.6 - 86.1)
Specificity (%)	66.67 (44.7 - 84.4)	91.67 (73.0 - 99.0)
Positive predictive value (PPV, %)	55.6 (30.8 - 78.5)	80.0 (44.4 - 97.5)
Negative predictive value (NPV, %)	84.2 (60.4 - 96.6)	81.5 (61.9 - 93.7)

Diagnostic indices are presented as value (95% CI).

¶DeLong method.

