- **(ROC) curve analysis for discrimination between patients with TTP/HUS or SPE/HELLP using the IPF-%:** The optimal cutoff values for IPF-% for discrimination between patients with TTP/HUS or SPE/HELLP was >15.9 %. The sensitivity and specificity were 76.92% and 66.7%, respectively. The positive predictive value (PPV) and negative predictive value (NPV) were 55.6 % and 84.2%, respectively (AUC=0.692) (**Table 18**) (**Figure 23**).

Assessment of Immature Platelet Fraction in Pregnancy-Associated Thrombotic Microangiopathy: (Results)

[figure not shown]

Figure (23): Receiver-operating characteristic (ROC) curve analysis for discrimination between patients with TTP/HUS or SPE/HELLP using the IPF.

Assessment of Immature Platelet Fraction in Pregnancy-Associated Thrombotic Microangiopathy: (Results)

- **(ROC) curve analysis for discrimination between patients with TTP/HUS or SPE/HELLP using the schistocyte count:** The optimal cutoff values for schistocyte count for discrimination between patients with TTP/HUS or SPE/HELLP was $>4.6\%$. The sensitivity and specificity were 61.54% and 91.67% , respectively. The positive predictive value (PPV) and negative predictive value (NPV) were 80% and 81.5% , respectively (AUC=0.771) (Table 19), (Figure 24).

[figure not shown]

Figure (24): Receiver-operating characteristic (ROC) curve analysis for discrimination between patients with TTP/HUS or SPE/HELLP using the schistocyte count.

Comparison of the receiver-operating characteristic (ROC) curves:

Comparison of the receiver-operating characteristic (ROC) curves between IPF-% or schistocyte count revealed no significant difference between IPF-% and schistocyte count regarding discrimination between patients with TTP/HUS or SPE/HELLP (P-value >0.05) (Table 19), (Figure 25).

Assessment of Immature Platelet Fraction in Pregnancy-Associated Thrombotic Microangiopathy: (Results)

Table (19): Comparison of ROC curves for discrimination between patients with TTP/HUS or SPE/HELLP using the IPF or schistocyte count

Index	IPF	Schistocyte count	Difference	z	P-value¶
Area under ROC (AUC)	0.692 (0.519 to 0.833)	0.771 (0.603 to 0.893)	0.079 (-0.171 to 0.328)	0.617	0.537

Diagnostic indices are presented as value (95% CI).

¶DeLong method.

Assessment of Immature Platelet Fraction in Pregnancy-Associated Thrombotic Microangiopathy: (Results)

[figure not shown]

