Figure (25): Comparison of ROC curves for discrimination between patients with TTP/HUS or SPE/HELLP using the IPF or schistocyte count.

Assessment of Immature Platelet Fraction in Pregnancy-Associated Thrombotic Microangiopathy: (Results)

Table (20): ROC curve analysis for discrimination between patients with TMA and normal controls using the IPF-%s or schistocyte count

Index	IPF-%	Schistocyte count
Positive group (TMA)	37 (64.9%)	37 (64.9%)
Negative group (normal controls)	20 (35.1%)	20 (35.1%)
Area under the ROC curve (AUC)	0.820 (0.695 to 0.909)	0.838 (0.716 to 0.922)
z statistic	5.678	8.660
P-value	<0.0001¶	<0.0001¶
Associated cut-off criterion	>8.1 %	>0 %
Sensitivity (%)	86.49 (71.2 - 95.5)	67.57 (50.2 - 82.0)
Specificity (%)	65.00 (40.8 - 84.6)	100.00 (83.2 - 100.0)
Positive predictive value (PPV, %)	82.1 (66.5 - 92.5)	100.0 (86.3 - 100.0)
Negative predictive value (NPV, %)	72.2 (46.5 - 90.3)	62.5 (43.7 - 78.9)

Diagnostic indices are presented as value (95% CI).

¶DeLong method.

- **(ROC) curve analysis for discrimination between patients with TMA or control using the IPF-%:** The optimal cutoff values for IPF-% for discrimination between patients with TMA or control was >8.1%. The sensitivity and specificity were 86.49% and 65%, respectively. The positive predictive value (PPV) and negative predictive value (NPV) were 82.1 % and 72.2%, respectively (**Table 20**), (**Figure 26**).

Assessment of Immature Platelet Fraction in Pregnancy-Associated Thrombotic Microangiopathy: (Results)

[figure not shown]

Figure (26): ROC curve for discrimination between patients with TMA and normal controls using the IPF.

- **(ROC) curve analysis for discrimination between patients with TMA or control using schistocyte count:** The optimal cutoff values for schistocyte count for discrimination between patients with TMA and normal controls was >0 %. The sensitivity and specificity were 67.57 % and 100%, respectively. The PPV and NPV were 100 % and 62.5%, respectively (**Table 20**), (**Figure 27**).

Assessment of Immature Platelet Fraction in Pregnancy-Associated Thrombotic Microangiopathy: (Results)

[figure not shown]

Figure (27): ROC curve for discrimination between patients with TMA and normal controls using the schistocyte count.

- **Comparison of the receiver-operating characteristic (ROC) curves:**

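### SAP Table 17 prints the >0% schistocyte counts under a >1% label and an impossible control count of 0.01; Table 15's control median of 0.01 does not match the values that were tested

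*SAP*

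**What the plan says.** - **SAP Table 17** has a row headed "High schistocyte count ($> 1" (percent), with 14 (58.3%) SPE/HELLP, 11 (84.6%) TTP/HUS and, for controls, 0.01 (0.0%). The footnote begins "Data are number", so each cell should be a count with a percentage. Fisher's P is given as <0.001.
- **SAP Table 6** has the same row headed "High schistocyte count (>0" (percent), with the same 14 and 11, and 0 controls.
- **SAP, ROC text for Table 20:** the optimal schistocyte cut-off for discriminating patients "with TMA and normal controls was >0 %. The sensitivity and specificity were 67.57 % and 100%, respectively". The table adds AUC 0.838 and z 8.660.
- **SAP, ROC text for Table 18:** at a cut-off of >4.6% for TTP/HUS against SPE/HELLP, "The sensitivity and specificity were 61.54% and 91.67" (percent).
- **SAP Table 15** gives schistocyte medians (IQR) of 0.5 (0.0-1.2) for SPE/HELLP, 6.5 (0.8-17.6) for TTP/HUS and 0.01 (0.0-0.03) for controls. Table 4 has the same patient values and the same Kruskal-Wallis statistic, 27.186, but 0.0 (0.0-0.0) for controls.
- **SAP Table 13** gives a control-group correlation between IPF and schistocytes of 0.000, with no P-value.
- **Protocol, Laboratory Investigations:** "Schistocytes counting will be performed in at least 1000 RBCs in optimal areas of the film".

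The SAP text after Figure 17 names Tables 14-22 as the ones that show the study's results.

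**The concern.** The same counts stand under two thresholds, and the version with the doubtful label is the one that readers are sent to. As printed, Table 17 says that 58% of SPE/HELLP and 85% of TTP/HUS women exceed 1% schistocytes. The schistocyte count is the marker against which IPF is compared throughout the ROC analyses, so its cut-off and its distribution in controls should be stated once and consistently.

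The control column raises a second question. A control median above zero does not sit with a specificity of 100% at >0%, so one has to ask which values entered the tests.

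**Working it through.** **1. Table 20 at >0%, from Table 17's counts.** Sensitivity = (14 + 11)/37 = 25/37 = 67.57% (exact 95% CI 50.2-82.0). Specificity = 20/20 = 100% (83.2-100). PPV = 25/25 = 100% (86.3-100). NPV = 20/32 = 62.5% (43.7-78.9). All match the printed values, so 14 and 11 are the >0% counts.

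**2. Upper limits at >1%, from Table 15.**
- SPE/HELLP, n = 24: the median is the mean of the 12th and 13th ordered values. With 13 or more women above 1%, both exceed 1% and the median cannot be 0.5. So at most 12, not 14.
- TTP/HUS, n = 13: with 11 women above 1%, the third ordered value exceeds 1%. Every standard quantile rule puts the first quartile at or above the third value, so it could not be 0.8. So at most 10, or at most 9 under rules that take the fourth value.

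**3. Lower limits at >1%.**
- SPE/HELLP: a third quartile of 1.2 needs the 19th value above 1%, so at least 6.
- TTP/HUS: 61.54% of 13 is 8 women above 4.6%, so at least 8. (For SPE/HELLP, 91.67% specificity leaves only 2 of 24 above 4.6%, a weaker limit.)

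| Group | Printed | Feasible at >1% | Overstated by at least |
|---|---|---|---|
| SPE/HELLP | 14/24 = 58.3% | 6-12/24 = 25-50% | 8.3 points |
| TTP/HUS | 11/13 = 84.6% | 8-10/13 = 62-77% | 7.7 points |

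**4. Fisher's exact test, three groups.** Printed counts with 0/20 controls: P = 1.2e-7. All feasible >1% combinations with 0/20 controls: P from 2.1e-6 to 1.4e-4. The printed <0.001 holds throughout.

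**5. Control values that entered the tests.** Set all 20 controls to zero, with 25 of 37 patients positive and 12 tied at zero:
- AUC = 25/37 + 0.5 × 12/37 = 0.838.
- DeLong SE: the patient components are 25 ones and 12 halves, and the control components are constant, so SE = 0.0390.
- z = (0.8378 - 0.5)/0.0390 = 8.660.

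AUC and z are both as printed. Table 13's control correlation of 0.000 without a P-value is also what a constant variable gives. Kruskal-Wallis is supporting evidence only: with these zeros and an AUC of 0.771, H is 27.18 (printed 27.186), but other patterns of zeros can give a similar value.

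**6. Table 15 against Table 4.** At one decimal, 0.01 (0.0-0.03) prints as 0.0 (0.0-0.0). Rounding for display is enough to reconcile these two cells. It is not enough for Table 20, where the controls must have been zero in the analysis itself.

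**7. If patient values were also rounded.** Table 6 leaves 10 SPE/HELLP and 2 TTP/HUS women at zero, which makes 10 × 2 = 20 tied pairs out of 24 × 13 = 312. Breaking all the ties one way or the other moves the AUC by 10/312 = 0.032, so 0.771 could lie anywhere in 0.739-0.803.

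**The case against.** The strongest case for leaving this alone is that it is one descriptive row for a comparator marker. The correctly labelled row is already in Table 6, Fisher's conclusion survives either threshold, and the study's aim concerns IPF-% and A-IPC. All of that is true and it limits the damage. It does not make the printed prevalences right for the printed threshold, or 0.01 a count.

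On Table 15, rounding is a fair defence. If values were recorded finely and rounded to one decimal before testing, with every control below 0.05%, Tables 4, 15 and 20 all stand. No rounding rule is stated, so this can be neither confirmed nor excluded. The counting rule does not settle it. At 1000 cells the step is 0.1%, and a median printed as 0.01 needs an 11th control value that is non-zero and below 0.03%, so more than 3,333 cells in that woman. The protocol sets only a minimum, so this is a reason to check and not proof of error.

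A reader might go further and infer that Table 20 is overstated. A non-zero control median means at least 10 of 20 controls above zero, hence specificity of at most 50% and AUC of at most 25/37 + (12/37) × 0.5 × (10/20) = 0.757 (z 4.18). The documents do not support this as the size of the error. The printed output shows that zeros were tested. The 0.757 also assumes 12 true patient zeros and every positive patient value above every control. With only 6-7 patient zeros and 10-11 non-zero controls, the best-case AUC is 0.853-0.878.

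**Conclusion.** Table 17's schistocyte row is wrong as written. Its counts are the >0% counts, and as >1% prevalences they are too high by at least 8.3 points (SPE/HELLP) and 7.7 points (TTP/HUS). Its control entry cannot be a number of women. This needs no assumption about rounding before analysis and follows from Tables 15, 17, 18 and 20 alone. The significance statement is unchanged, provided that no control exceeds 1%.

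Table 15's control cell does not describe the values that were analysed. It is either a wrong cell or an unrounded value whose rounded form was tested, and the documents do not say which. A loss of specificity or AUC in Table 20 is not shown.

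The TTP/HUS against SPE/HELLP schistocyte results stand if only the label and the control cells are at fault. They are not guaranteed if patient values were rounded too (AUC 0.739-0.803 around the printed 0.771). Results that use IPF alone are unaffected in every case.

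**What to change.** 1. In Table 17, either relabel the row >0%, or report the true counts, percentages and Fisher's P at >1%. Replace 0.01 with the true number of controls.
2. Check Table 15's control cell, and the precision at which schistocytes were counted, recorded and analysed, against the patient-level data. Then:
   - if all controls are zero, restore 0.0 (0.0-0.0) in Table 15;
   - if values were rounded before testing, say so, use one precision throughout, and describe the >0% cut-off at that precision;
   - if non-zero values below 0.05% are real and should enter the tests, re-run the schistocyte analyses at that precision. This covers the control-dependent results (Tables 4, 6, 9, 10, 13, 15, 17, 20, 21) and, if patient values were also rounded, the patient-only ones (Tables 12, 18, 19, 22-25, with Tables 7 and 8, which repeat 18 and 19).

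The cost is re-tabulation of existing data and, at most, a re-run of existing tests. No new patients or measurements are needed.
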